#### 6.3.2: Packing and storage.

The cheese will be delivered in 250-gram packages from Tine. The Jarlsberg cheese and the supplements used in the study will be given free of charge to the patients. Each package is labeled in accordance with the procedure for clinical trials. Additionally, the participants will be informed on how to perform the intake of the cheese and to store the cheese in a refrigerator at a temperature from 4° to 10°C. Expiry date will be printed on the label.

**Table IIV: Label on each package**

Description	For use only in clinical trial
Trial substance	Jarlsberg® Original
Expire date	
Administration	Oral intake
Investigator	
Name of exporter	TINE A/S:
[contact]
Study	Comparative study in risk patient for Osteoporosis
EudraCT number	
Protocol id	PF-Jarlsberg/IIIA
Storage	Refrigerator between 4° to 10°C

#### 6.4: Stopping rule

In case of life-threatening AE or Serious Adverse Events (SAE) occurs, the cheese intake must stop, and the patient treated and followed up in accordance with GP-center routines.

#### 6.5: Procedures for Blood sampling and analysis.

Blood will be drawn from the fasting patients via a cubital vein and separated into serum by centrifugation. Two ml serum will be sending Vitas for Osteocalcin analysis and 2 ml send for K2 analysis at the biochemical laboratory of NMBU. The blood samples for measurements of the hematological and biochemical variables will be handled in accordance with the standard procedures at the GP-center and send to Fürst laboratory and The Hormone laboratory of Oslo University Hospital in Oslo for analysis.

#### 6.6: Report of serious adverse effect (SAE)

The participant will be advised to contact the investigator if she suffers from severe AE or any other annoying conditions.

[figure not shown]
In case of SAE, the investigator must complete the SAE form and send it to the health authorities with copy to TINE and the study manager [name] within 24 hours.

[name] [name]  
 Meddoc AS  
 [name]  
 Office: [name]  
 [contact]  
 E-mail: [[contact]](mailto:[contact])

#### 6.7: Time schedule

A patient recruitment period of 12 months may be needed. The duration of each included patient will be between 32 and 48 weeks. The total duration of the study will be as follows:

Inclusion of the first patient	15-06-2023.
Inclusion of the last patient	15-06-2024.
The first patient finalized	15-01-2024.
The last patient finalized	15-12-2024.
Closing database	15-09-2025.
Finalized Clinical Study Report	15-10-2025.
Draft of manuscript for publication	15-12-2025.
One Year follow-up period	15.01.25 – 15.12.25.

x) is related to the patients initially allocated to only Calcium + vitamin D (Control group)

## **VII: Project management and Monitoring**

### **7.1: Project management**

The study will be administered by a Steering committee headed by [name] [name] and consist of [name] [name], [name] [name], and [name]. The study will be monitored by a CRA from Meddoc. The data manager for this study will be [name] Meddoc Biometric Group, Norway and coordinated by [name] [name] and [name] [name]. [name] will be responsible of the Data Management and the Statistical Analysis and [name] for the laboratory analysis. The steering committee will have a joint responsible for publication of the results in international journals.

### **7.2. Quality assurance demands.**

The validated data management (DM) system InCRF will be used for electronically collecting the data. The system selected is compliance with GCP guidelines and subject to 21 CFR (Code of federal regulations) FDA part 11 requirements. All the data created in this study will be entered at site, stored, and monitored electronically. The study case record forms (CRF) will be available at the DM-system and the data entered directly into the system at the site. Monitoring will be performed electronically and copies of the laboratory results and printed eCRF with Investigator's signature will be the source-documents.

In conducting the trial, TINE as the Sponsor accepts that the Ethics Committee or regulatory body may, at any time by appointment, conduct an audit of the study site, the laboratories conducting any clinical testing or the GMP manufacturing facilities.

### **7.3: Start-up and closing visit**

The project manager and the clinical monitor will perform the start-up visit at the participating site. The visit will consist of a site inspection, information, instruction and handing the CRFs.

The project manager and the clinical monitor will perform the closing visit within one month after the last participant has finalized the study. All the trial material will be removed from the site.

### **7.4: Monitoring procedure**

Essential demographic data will be documented with the participants' record notes as the source data and send to the monitor by e-mail after entering the InCRF-system. Source data will also include the date of written consent, times and dates of blood sampling and physical examinations.

It is the responsibility of the investigator to maintain accurate and up to date records of all clinical trial related activities, which should be legibly entered onto the CRFs provided. The CRFs should be made available in the event of a formal investigator site audit.

The site will be monitored seven times during the study. This includes both the start-up and the closing visits. Monitoring report will be sent to the project manager for every site inspection.

### **7.5. Curriculum vitae**

All involved researchers participating in the study must show an updated CV documenting their expertise in the relevant clinical field. The CV must be signed and dated by the

physician and a copy must be attached to the protocol if required according to international rules. Another copy should be kept in The Trial Master File and a third copy in the Site File.

#### **7.6. Site File**

Meddoc will supply the investigator with a Site File. The Site File should contain all documents relevant for the study. The investigator is responsible to keep the Site File updated and secure that all required documents are present in the File. The Site File will be inspected during the monitor visits.

#### **7.7. Fees**

Neither the project manager nor study employees will receive special remuneration for their participation in the study. They are fast paid from their respective institutions. In contrast, the study budget earmarks NOK 20,000 for the scientific panel. The participating doctors, including laboratory staff who carry out the clinical work, receive NOK 11 000 per patient. The professionals named in the protocol will be remunerated through participation in all publication and presentation of results from studies. The participating patients will not receive any fee for participation, but the study will cover extra travel expenses in connection with visiting the doctor and other examinations in the study.

## VII. Consideration

### 8.1: Consideration of steering committee

The study will be carried out according to the Helsinki declaration with latest amendments, Good Clinical Practice (GCP) and International Ethical Guidelines for Health-related Research Involving Humans (CIOMS guidelines). The participants are risk patient for Osteoporosis and will only be included in this clinical trial after approval of the trial by the regional Ethical Committee (REK) and the patients have received oral and written information and signed informed consent.

The product to be used in this trial is Jarlsberg cheese commercially available in Norway. To the best of our knowledge, no AE is reported except from person with intolerance of milk and milk product. It is known that vitamin K2 passing a certain daily dose may increase and strengthen the bone density and may therefore have a prophylactic effect on bone fracture. Jarlsberg cheese is shown to be one of the Norwegian produced cheeses with the highest level of vitamin K2.

In a previously conducted dose-response study on healthy fertile women we found the optimal efficacy dose (OED) to increase the osteocalcin levels. Our hypothesis is that this effect is caused by the fermentation of lactic acid to propionic acid by the *Propionibacterium freudenreichii* in the Jarlsberg Cheese, producing MK 9-4H K2 vitamer and DHNA. The first aim of this study is to compare the effects with the commonly used prophylactic treatment of vitamin D + calcium to verify the hypothesis. Our second aim is to study the development of BTM and BMD by the OED of Jarlsberg Cheese and to verify if the cheese could be recommended as prophylactical treatment to osteoporosis.

All participants invited to this clinical trial are entitled to make their decision based on the fullest amount of information available at that time. To make the choice, they will be given a written document expressed in a clear concise language of their native tongue to consider. The document will tell potential participants about the aim of the study. Additionally, that blood sampling will be performed between five and seven times in connection with clinical examinations during the two study parts.

*Summary:* All the included patients will receive the daily intake of cheese, supplement, and clinical examinations free of charge. All participants will be given oral and written information and must give their written consent to participate in the study. To the best of our knowledge, this study fulfils the entire international requirement to an ethical controlled clinical trial.

### 8.2: Approval of the project

This study will be performed in Norway and the study protocol together and other requested information will be sent for approval by Regional Ethical Committee (REK). Inclusion of participants will not be started before the approval is received.

The database and storage will be in Norway and must be approved by the Norwegian Centre of Research Data” (NSD).

### **8.3: Informed consent**

Before the start of the trial, the investigator will explain the confidentiality of participation in this research project, the objectives of the trial, the specific requirements for the patients, the trial design, and the consequences of participation. Additionally, the investigator must obtain written informed consent from the participants before inclusion in the study.

### **8.4: Protection of personal data**

The monitor may know the identity of the participants during verification of the source data. However, the monitor has unconditional professional secrecy.

All participant-related material leaving the trial site will be anonymous so that the patients only can be identified by date of birth, initials, and study identification number. The investigator is responsible for keeping a list with the full names, their citizens' number, and corresponding study numbers according to the demands in GCP.

The participants will receive all the Jarlsberg cheese + supplements and the clinical examination for free.

In accordance with Norwegian and international roles, the data from this study will be stored in at least 15 years.

## **IX. Data Management**

### **9.1: Electrical Case Record Forms (eCRF)**

The validated electrical data management system InCRF will be used for collecting the data. Mainly the data will be entered on eCRFs by the responsible investigator at stage. Prior to study start; a data entry instruction document will be made. In this study a copy of source data will be collected on a paper. Source data consist of both printouts from the laboratory. In case of printing CRF data from InCRF instead of using paper CRF, it is important that also these are stored. The printed CRF data need investigator's signature and date.

### **9.2: Study Database**

The validated data management system InCRF will be used for collecting the CRF data. The system selected is compliant with GCP guidelines and subject to 21 CFR (Code of federal regulations) FDA part 11 requirements. The final database will be stored in the Statistical Analysis system (SAS ver. 9.4 or later).

### **9.3: Data handling**

The DM will perform the data checks. Once all the errors or issues are corrected or resolved, the investigator shall sign all the eCRFs to acknowledge all the data in the database has reviewed and corrected. After all the eCRFs has electronically signed by the investigator, the Study Statistician will perform final SAS checks and proof reading of safety listing.

Thereafter, the database can perform final database hard lock.

The database will be transformed to a labelled SAS database, which also will be locked to prevent all possible changes or additions. In this copy, the responsible statistician can make derivations but no corrections of the data. If corrections are needed, the main basic study database must be re-opened and corrected. The international procedure for such changes will be followed.

## **X: Discontinuation of treatment**

A patients may discontinue from the study at any time if in the view of the investigator it is in the patient best interests. Alternatively, the patient has the right to discontinue the consent and exit the study without prejudice regarding his/her future treatment or care.

If a patient doesn't show up to an agreed visit the investigator should try to motivate the patient to continue.

### **10.1: Discontinuation not related to the study question**

If patient discontinue the study of administrative reasons or reasons documented not related to the trial treatment will be classified as "Drop out" and replaced by new participant. The dropouts will be described specially in the statistical analysis.

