### 1.6: Design and randomization

#### 1.6.1 Design:

The study will be performed as a randomized, single-blinded Norwegian multicentre trial with stratified semi-cross-over design with gender and participating General Practitioner (GP) site as stratification factors. 10 GP's from Viken county will participate.

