### 1.8.2 Clinical part

The patients will be allocated (1:1) to vitamin D + Ca-tablets  $\pm$  Jarlsberg cheese. All the participants will get new delivery of vitamin D and Ca-tablets every four weeks. The patients allocated to Jarlsberg will additionally receive Jarlsberg cheese. The patients will receive a compliance & activity form and asked to fill in every day. All the patients meet for new visits at week 4, week 16, and week 32. Patients allocated to only vitamin D + Ca tablets at baseline well additionally meet for visits at week 20 and week 48. At all these visits blood samples for

measurement of Osteocalcin, CTX-1, PINP, BALP and PTH will be drawn fasting in the morning, and concomitant medication and treatment compliance recorded. The main visits will be performed every 16 weeks. New DXA screening will be performed. Patients obtaining a BMD T-score  $\leq -2.5$  will discontinue the study and switched to antiresorptive treatment plus daily OED of Jarlsberg cheese. The daily food intake during four consecutively days will be recorded on the Diet-App. Blood samples for measurements of Osteocalcin, CTX-1, PINP, BALB and PTH will be drawn fastening in the morning at every visits. Furthermore, blood samples for measuring and biochemical variables, HbA1C and Lipids, will be recorded. The CTCAE will be recorded as well. The visit at Week 32 and Week 48 will be the last observation in the study for the patients initially allocated to Jarlsberg and controls, respectively. In addition to the mentioned variables blood samples for measurement of Interleukins and Cytokines will be performed. All the patients completed the study will be offered to continue the daily intake of Jarlsberg cheese. These patients will be followed up one year after the last visit with a new DXA and a blood sampling for measurements of the Osteocalcin level and the bone markers PINP, CTX and BALP.

**1.9: Sample size:** With a significance level of 5%, a power of 90% and a Clinically Relevant Difference (CRD) of one time the Standard Deviation in change of BMD, at least 24 patients in each group must finalize the study. With an expected drop-out rate of 25%, 30 patients in each group must be included.

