## IV: Design and randomization

### 4.1: Study design

The study is performed as an open randomized semi crossover design with two strata. Sex is used as a stratification factor (Figure 1). The two strata are chosen because of different OED of cheese for women and men. Within each stratum the participants will be allocated either to vitamin D + Calcium alone (Control) or with daily OED of Jarlsberg cheese (Jarlsberg). The two groups will run parallelly in 16 weeks and BMD recorded by DXA. Patient with T-score < -2.5 classifies as Osteoporotic patients will be withdrawn from the study. At week 16, the patients in the control-group will be switched to additional daily OED of Jarlsberg cheese for 32 weeks. The patients randomised to Jarlsberg will continue with the same treatment for additionally 16 weeks.

[figure not shown]

Figure 2: Study design with time schedule and variables to be recorded. Measurements given in red (x) is related only to the patients initially randomised to only vitamin D + Ca (control).

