### **10.2: Discontinuation related to the study question**

If patient discontinue the study of reasons related or might be related to the trial treatment will be classified as "Withdrawal". These will not be replaced by new participants but included in both the Per-Protocol (PP) and the ITT analysis using the procedure "Last observations carried forward" (LOCF).

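### Section 10.1 replaces randomised patients whose exit is recorded as unrelated to treatment and, by contrast with 10.2, implies that they leave the ITT set

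*Protocol*

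**What the plan says.** Protocol section X sorts discontinuations by their reason.

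- **Section 10.1 (Drop out).** This class covers administrative reasons and reasons documented as unrelated to the trial treatment. Such a patient is "replaced by new participant. The dropouts will be described specially in the statistical analysis". No analysis set is mentioned.
- **Section 10.2 (Withdrawal).** This class covers reasons that are related, or might be related, to treatment. The rule is: "These will not be replaced by new participants but included in both the Per-Protocol (PP) and the ITT analysis using the procedure" of last observation carried forward.
- **Who judges.** The opening of section X says that a patient may "discontinue from the study at any time if in the view of the investigator it is in the patient best interests". That concerns the decision to stop. Nobody is named as classifying the reason, and no blinded assessment of it is described.
- **Blinding.** Section 4.1: "The study is performed as an open randomized semi crossover design with two strata". Section 1.6.1: "randomized, single-blinded Norwegian multicentre trial", without saying who is blinded. Under section 1.5 the control group receives tablets only.
- **Sample size.** Section 1.9 asks for 24 completers per group and adds: "With an expected drop-out rate of 25%, 30 patients in each group must be included". Section 11.3 gives the same 24 and 30, but says that the increase also allows for the multicentre situation.

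**The concern.** An intention-to-treat comparison is protected because membership is fixed at randomisation. Here the two rules are worded as alternatives: one class is replaced and described, the other is not replaced but included. A reader applying them would build an ITT set of randomised patients, minus those whose exit was recorded as unrelated, plus substitutes.

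The recorded reason arises after randomisation, and patients know whether they are eating the study cheese. Only one arm has a daily cheese portion during the 16-week comparison, so both the reasons for leaving and the way they are recorded can differ by arm. If they also relate to response, the comparison of BMD and bone markers is no longer a comparison of the groups as randomised, although the table would be labelled ITT.

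There is a related gap for Aim 3, time to recommended osteoporosis treatment. Patients who reach the T-score limit leave the study, and section X does not say which class they belong to.

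**Working it through.** **1. The two rules side by side**

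| | 10.1 Drop out | 10.2 Withdrawal |
|---|---|---|
| Reason | administrative, or documented as unrelated | related, or might be related |
| Replaced | yes | no |
| ITT and PP | not mentioned; described only | included in both, by LOCF |

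No other section places drop-outs in an analysis set. Exclusion is therefore an inference from the contrast, although it is the natural one.

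**2. The plan's own sample size**

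Inputs: difference 1 SD, alpha 5% (two-sided assumed, since sidedness is not stated), power 90% (section 1.9) or 95% (section 11.3).

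n per group = 2(z₁₋α/₂ + z₁₋β)² / 1²

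- 90%: 2 × (1.960 + 1.282)² ≈ 21.0, so 22 (23 with the t-test).
- 95%: 2 × (1.960 + 1.645)² ≈ 26.0, so 26 (27 with the t-test).

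The stated 24 lies between these and has t-test power of 92.4%.

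Drop-out allowance: 24 × 1.25 = 30 is the stated figure, whereas 24 / 0.75 = 32 would leave 24 completers after a 25% loss.

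**3. What happens without replacement**

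- 30 × 0.75 = 22.5 completers per group, below 24. The t-test power for 1 SD is 90.6%.
- All 30 per group with an outcome: 96.8%.

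The 90% in section 1.9 therefore does not depend on replacement. The 95% in section 11.3 would not be met by completers alone, and 24 completers do not meet it either.

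**4. What happens with replacement**

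If all of the 25% loss were replaced until 30 per group remained, 30 / 0.75 = 40 per group would be randomised. That is 80 in total, of whom 20 would be replaced. This is an upper case, because some exits would be Withdrawals.

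**5. Illustration of selection (assumed; the Protocol gives no such figures)**

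No true effect and 30 analysed per arm. In the cheese arm, 30 + m patients are randomised, and m of them, drawn at random from the lower-responding half, are recorded as unrelated exits and replaced. No selection among controls. Two-sided 5% t-test, 20,000 simulated trials.

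The lower half of a normal distribution has mean −0.798 SD, so the expected bias is about m × 0.798 / 30.

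| m | Formula | Simulated bias | Rejection rate |
|---|---|---|---|
| 3 | 0.080 SD | 0.080 SD | 5.9% |
| 6 | 0.160 SD | 0.157 SD | 8.5% |

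**6. What a corrected ITT can recover**

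In the flow chart (section 1.11), the first DXA after baseline is at week 16 and the first marker sample after baseline is at week 4. A patient who leaves before week 16 has no observed BMD change whichever set he or she is in.

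**The case against.** The best defence is that 10.1 never says drop-outs are removed from ITT, and that set definitions may stand in an SAP that is not shown. That is right as far as it goes: exclusion is implied, not stated. But the replacement rule, and its contrast with 10.2, are fixed in the Protocol, so the ambiguity is the Protocol's to remove.

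A second defence is that 10.1 requires a documented unrelated or administrative reason, while 10.2 takes anything that might be related. Doubtful cases therefore go to 10.2 and stay in ITT. Someone who stops because of the daily cheese portion belongs there. This stands and narrows the exposure. It does not remove the dependence on a post-randomisation judgement.

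Several stronger readings are tempting but not supported:

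- **That patients reaching the T-score limit would be replaced and their Aim 3 events lost.** Sections 4.1, 6.2.2 and 6.2.3 call these patients withdrawn, which points to 10.2. The criterion in 10.2 is relation to treatment, which need not fit disease progression, so the class is unclear. No section makes them replaceable.
- **That replacement is redundant.** 30 with 25% loss leaves 22.5, below 24, and section 11.3 uses the increase for the multicentre situation as well.
- **That the bias favours the sponsor's product.** Nothing in the documents establishes a direction.
- **That the error rate could reach about 25%.** This needs 25% of the cheese arm replaced, those patients averaging 1 SD below the arm mean (bias 0.25 × 1 / 0.75 = 0.33 SD), and no selection among controls. It is a stress case.
- **That the trial is simply unblinded.** Section 4.1 says open and section 1.6.1 says single-blinded. The two must be reconciled, though without placebo cheese patients know their group in either case.

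**Conclusion.** The point holds in a limited form. Section 10.1 replaces randomised patients according to a reason recorded after randomisation and, by contrast with 10.2, implies that they are left out of ITT. No blinded classifier is named, the Protocol contradicts itself on blinding, and the control arm has no placebo cheese.

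The fault is in the rule and does not rest on a number. The type I error of about 6% to 9% illustrates mild one-arm selection under stated assumptions and is not a forecast. Neither the amount nor the direction of bias can be derived from the documents. Correcting the rule would reduce selection bias for BMD but not remove it, because exits before week 16 remain missing data. The class of patients who leave on reaching the T-score limit is an ambiguity to settle, not a demonstrated loss of events.

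**What to change.** Amend section X before outcomes are known:

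1. State in 10.1 and 10.2 that ITT is every randomised patient in the allocated arm, whatever the reason for stopping, using all BMD and marker values obtained.
2. Delete the replacement in 10.1. If it is kept, state that a new participant takes the next randomisation number as an additional patient and never substitutes in ITT for the patient who left.
3. State that patients without a week-16 DXA are counted in ITT, by arm and reason, and handled as missing data.
4. State which class a patient withdrawn on reaching the T-score limit falls in, so that this Aim 3 event is retained in the analysis. No clinical rule needs to change for this.
5. Reconcile sections 1.6.1 and 4.1 on blinding.

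The cost is a few sentences and possibly fewer completers. Without replacement, a 25% loss leaves 22.5 per group against the stated 24. That still gives about 90% power for a 1 SD difference, in line with section 1.9, but not the 95% in section 11.3.
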